- Necessitates medical or surgical intervention to preclude a permanent disability or incapacity
- Results in a congenital anomaly or birth defect

Non-serious adverse events are all events that do not meet the criteria for a “serious” adverse event.

Severity:

Each adverse event will be assessed for its severity, or the intensity of an event experienced by the subject, using the following.

- Mild: Discomfort noticed, but no disruption to daily activity.
- Moderate: Discomfort sufficient to reduce or affect normal daily activity.
- Severe: Inability to work or perform normal daily activity.

Anticipated Adverse Events and Pre-existing conditions:

Pre-existing conditions will not be reported as an adverse event unless there has been a substantial increase in the severity or frequency of the problem which has not been attributed to natural history.

Data Handling and Recordkeeping

Each subject's name, birth date, address and phone number will be obtained for purposes of follow-up. We will ask for each subject's drug use history, medical history, and current drug use. Experimental data and questionnaire data will be collected. This information will be coded into the Microsoft Excel. Each subject's personal information will be de-identified in the database by using codes comprising the subject number and date and time the subject was tested. The PIs and study personnel at UAMS and UCA will have access to subject identities in order to arrange follow-up and to call them as part of the research project, such as follow-up contact. If subjects prefer e-mail correspondence research personnel will send e-mails for scheduling, follow-up, and research-related communication.

Data Analysis

Aims 1-3. Difference scores from baseline will be calculated for each outcome measure. A mixed model ANOVA with group (active tDCS groups versus sham tDCS) as the between subjects factor and time of assessment (pre, weeks 1-4, & one week and one month post) as the within subjects factor will be used to test all aims. A significant group effect, with active tDCS > sham tDCS, for any of the outcome measures would indicate that anodal tDCS augments gait training. A significant main effect of time would be evaluated using planned contrasts where we expect post treatment assessments to be improved relative to baseline. Interim analyses will be completed at critical stages during the protocol.

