Power analysis: We aim to determine whether tDCS can augment the beneficial effect of gait training. Our preliminary study using tDCS to improve gait velocity and the SIS16 score yielded very large effect sizes for walking speed (2.95) and the SIS16 (1.32). In real terms, patients who received active tDCS reduced their time to walk 10 meters by about one minute (this could shave 5 minutes off a task, like getting mail, so it is functionally significant); whereas those who received sham reduced their time by only 10 seconds. Power calculations indicate that sample sizes = 11 will yield power of .95 and .80, respectively, to detect a tDCS-induced improvement gait velocity and physical function. However, assuming a very large effect size of greater than 2 is likely unrealistic. Therefore, we based our power analysis on determining a substantial meaningful change in gait speed (0.1 m/s) as determined by Perera et al.⁴⁸ Using a 2 x 3 mixed MANOVA with interaction and an estimated effect size of (Cohen's $d =$

Version 10 Revised 11/21/2014

0.39)³⁷, a conservative $r = 0.60$ ⁴⁹ and an alpha of 0.05 we will need 37 subjects per group to achieve a power of 85%. Therefore, we set our sample size at 88, so our study has sufficient power to detect meaningful changes in gait speed for individuals with chronic stroke.

We set our primary study sample size at 88, so our study has sufficient power to detect a benefit of gait training and to determine if tDCS augments improvement.

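### The stated 85% power at 37 per group does not follow from its own inputs, and it is for an interaction rather than the group effect the analysis tests

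*Combined protocol and SAP*

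**What the plan says.** The sample size rests on one calculation in Data Analysis, Power analysis. The pilot effect sizes are set aside there as probably unrealistic. The calculation is then based on a meaningful gait-speed change of 0.1 m/s: "Using a 2 x 3 mixed MANOVA with interaction and an estimated effect size of" Cohen's d = 0.39, with r = 0.60 described as conservative. The result is that at "an alpha of 0.05 we will need 37 subjects per group to achieve a power of 85" per cent.

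The section draws its conclusion twice: "Therefore, we set our sample size at 88, so our study has sufficient power to detect meaningful changes in gait speed", and again "We set our primary study sample size at 88, so our study has sufficient power to detect a benefit of gait training".

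The planned analysis is in Data Analysis, Aims 1-3. It states "Difference scores from baseline will be calculated for each outcome measure" and specifies a mixed model ANOVA with "time of assessment (pre, weeks 1-4, & one week and one month post) as the within subjects factor". The efficacy criterion is "A significant group effect, with active tDCS > sham tDCS, for any of the outcome measures". The group-by-time interaction is not named as the deciding test.

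The Protocol Summary and Post-Intervention Procedures give gait speed a baseline and six later assessments (weeks 1 to 5 and week 8). Study Population asks for 88 completers, 44 per group, with dropouts replaced.

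**The concern.** There are two problems.

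- **The figure does not follow from its inputs.** A group difference of 0.39 SD is modest, and 37 per group is few for a two-degree-of-freedom interaction at r = 0.60. A power of 85% looked too high.
- **The figure is for another test.** The plan powers an interaction over three unnamed time points but decides on a group effect in change scores over more assessments. The two tests are related, but their power differs.

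The effect size cannot be traced either. No gait-speed SD is given, the step from 0.1 m/s to 0.39 is not shown, and the reference attached to 0.39 is, by its title, a Rasch analysis of the Stroke Impact Scale.

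This is the only support for saying that 88 patients are enough. If power is lower than stated, a null result could be misread as evidence that tDCS adds nothing meaningful.

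**Working it through.** **Inputs from Power analysis:** 2 groups, 3 times, interaction, d = 0.39, r = 0.60, alpha 0.05, n = 37 per group (N = 74).

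**Not stated, so assumed:** two-sided test; groups equal at baseline; group difference rising to d, either gradually (0, d/2, d) or in full from the first post-baseline time (0, d, d). All results below are therefore illustrative.

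**Step 1. The stated 2 x 3 interaction.** Hotelling T² with noncentrality lambda = (n/2) v'V⁻¹v and df (2, 2n-3), where v is the group difference in change scores and V their covariance. Under compound symmetry, lambda = (n/2) x (sum of squared deviations of the pattern from its mean) / (1-r).

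- Full: 18.5 x (2/3 x 0.39²)/0.4 = 18.5 x 0.1014/0.4 = 4.69; power 46.0%.
- Gradual: 18.5 x (1/2 x 0.39²)/0.4 = 18.5 x 0.07605/0.4 = 3.52; power 35.7%.

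Simulation of 20,000 trials gives 46.2% and 35.4%. If d is on the change-score SD, the difference in raw SDs is 0.39 x sqrt(2(1-0.60)) = 0.39 x sqrt(0.8).

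| Reading, 37 per group | Gradual | Full |
|---|---|---|
| Compound symmetry, raw SD | 35.7% | 46.0% |
| Compound symmetry, change-score SD | 29.3% | 37.8% |
| Decay, baseline/week 5/week 8, r = 0.60 from baseline to week 5 | 27.6% | 36.6% |
| Same visits, r = 0.60 from baseline to week 8 | 37.3% | 50.3% |
| Decay, equal spacing, r = 0.60 between neighbours | 23.6% | 37.0% |
| Decay, equal spacing, r = 0.60 from first to last | 35.7% | 58.9% |

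At 44 per group the first two rows become 41.9% to 53.5% and 34.3% to 44.3%. At 37 per group, 85% needs lambda = 11.40. Under compound symmetry that is 0.39 x sqrt(11.40/4.69) = 0.61 SD (full) or 0.39 x sqrt(11.40/3.52) = 0.70 SD (gradual).

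**Step 2. Where 85% could have come from.** Software-style entries with N = 74; the implied difference is 0.39 x sqrt(lambda/4.69) (full) or 0.39 x sqrt(lambda/3.52) (gradual).

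| Entry | Lambda | Power (MANOVA / univariate df) | Implied difference, full / gradual |
|---|---|---|---|
| f = d/2, 3Nf²/(1-r) | 21.10 | 98.6% / 98.8% | 0.83 / 0.96 SD |
| f = d/2, Nf²/(1-r) | 7.03 | 63.8% / 64.8% | 0.48 / 0.55 SD |
| f = 0.39, Nf², r unused | 11.26 | 84.5% / 85.3% | 0.60 / 0.70 SD |

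The last row is a likely but unproven origin. It treats 0.39 as f although the plan calls it d, and it ignores the r that the plan lists.

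Two other routes land near 85%, and neither rescues the statement:

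- A crossing pattern (-d, 0, d) has lambda = 18.5 x (2 x 0.39²)/0.4 = 14.07 and power of about 92%. On the change-score SD, lambda is 14.07 x 0.8 = 11.26, which gives 84.5%. It requires the groups to differ by d at baseline in the wrong direction.
- A baseline-adjusted comparison of the mean of six visits gives 84.8% at 37 per group. It is not a 2 x 3 interaction, and the plan has no baseline covariate.

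**Step 3. The planned test.** A t test on each patient's mean of six change scores, df = 2n-2, n = 44. A pre level would be zero for everyone on difference scores, so including it rescales mean and SD alike and leaves power unchanged. The mean effect is 0.39 (full), or 0.39 x (1/4 + 1/2 + 3/4 + 1 + 1 + 1)/6 = 0.2925 (gradual). Under compound symmetry the variance of the mean is (1 + 5r)/6 + 1 - 2r = 0.467. The noncentrality is 0.39/sqrt(0.467 x 2/44) = 2.68 (full) or 2.01 (gradual).

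| Reading, 44 per group | Gradual | Full |
|---|---|---|
| r = 0.60, compound symmetry, raw SD | 51.0% | 75.4% |
| Same, change-score SD | 42.7% | 65.8% |
| Decay, r = 0.60 from baseline to week 5 (variance 0.4035) | 57.0% | 81.3% |
| Decay, r = 0.60 from baseline to week 8 (variance 0.2775) | 73.1% | 93.0% |
| r = 0.50, compound symmetry, raw SD | 42.7% | 65.8% |
| r = 0.70, same | 63.0% | 86.4% |
| r = 0.80, same | 80.2% | 96.3% |
| r = 0.60, compound symmetry, raw SD, one-sided | 63.6% | 84.4% |

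Simulation of the first four rows agrees to within 1 point.

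**Step 4. The SD behind d.** If d is 0.1 m/s over the raw SD, that SD is 0.1/0.39 = 0.256 m/s. If d is on the change-score SD at r = 0.60, the raw SD is 0.256/sqrt(0.8) = 0.287 m/s. Neither is stated.

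**The case against.** The strongest reply is that the plan is under-specified rather than wrong. It never says that d is the largest between-group difference. Over all readings, interaction power runs from 24% to 99%, which brackets 85%, and entering 0.39 as f matches the stated design, sample size and alpha almost exactly. That stands as a probable explanation. It does not support the text, because it needs a different effect-size measure and drops one of the listed inputs.

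A second reply is that a group effect on change scores is a one-degree-of-freedom part of the raw-score interaction. Three time points also fit the schedule for the recruitment curve and the Stroke Impact Scale. Both points are fair, so the calculation is not unrelated to the analysis. But it was made for gait speed, which has seven assessments, and degrees of freedom and power both differ.

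Third, r = 0.60 is called conservative, and 88 completers exceed the 74 calculated. Higher correlations, or decay with r = 0.60 reaching week 8, can take the planned test above 85%. This also stands: a shortfall is not demonstrated. The step from 37 to 44 (37/0.85 = 43.5) fits the 15% attrition allowance, but it does not repair the 85%.

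**Conclusion.** The concern holds, and the statement is wrong as written. Where the groups start equal and their difference rises to 0.39 SD, no reading tried exceeds 59% for the interaction at 37 per group. The f = d/2 entries miss 85% in both directions. The entries that come close depart from the stated inputs, start from an adverse baseline difference, or belong to another analysis.

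The figure is also not for the test that decides efficacy. For that test at 44 per group, two-sided with r = 0.60, the illustrative range is 43% to 93%, and 51% to 75% under compound symmetry on the raw SD.

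Confidence is high that 85% is not supported by the stated inputs. It is not high for any single replacement figure, because each depends on the SD scale, sidedness, effect pattern and correlation structure, which the plan does not give.

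**What to change.** Replace the 85% statement in Power analysis with power recomputed by the sponsor for the group effect on change from baseline at 44 per group. State the gait-speed SD, how d was obtained from 0.1 m/s and on which SD scale, sidedness, time points, effect pattern and correlation structure, and show a range of r. Suggested wording, with blanks for the sponsor's values:

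> With 44 completers per group, power for the group effect on change from baseline in gait speed over the six post-baseline assessments is [ ]% at r = 0.60 and [ ]% to [ ]% for r from [ ] to [ ], assuming a difference of 0.1 m/s, SD [ ] m/s (d = [ ] on the [raw / change-score] SD), [one/two]-sided alpha 0.05, [correlation structure] and [effect pattern].

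If the interaction calculation is kept, name the routine, its effect-size measure and its three time points. Check the reference attached to 0.39. Remove or qualify both claims of adequate power unless the new figure supports them.

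The cost is one rewritten paragraph, with no extra patients and no change to eligibility, conduct or analysis. The stated power may become less favourable.

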Prior to the MRI scan, subjects may have a training session in the MRI simulator to help habituate and train them to the MRI environment. Per the MRI Policies and Procedures, the decision of who will be acclimated in the MRI Simulator will be made by the Research Coordinators and PI on a case-by-case basis. The PI for the study will have final say in this decision. Before the MRI scan, participants will be given an explanation of the study's procedures and screened with the MRI Safety Form for metal objects and claustrophobia. Participants will also be screened with the SAFESCAN® ferromagnetic detector according to MRI Policy and Procedures. The participant will then lie supine in the scanner. Participants will wear noise-cancelling headphones for communication and view visual stimuli through a mirror attached to the imaging head coil. Participants will undergo an anatomic scan to facilitate alignment of electrodes. Participants will also have a resting state scan in which they will be told to simply let their mind wander while they lay still in the scanner. Participants will also complete a scan measuring TA contraction. Subjects will be asked to contract the TA muscle in their right and left legs periodically depending on stimuli presented to them. Participants will have an identical repeat fMRI scan after completing the gait training protocol. Total scan time will be approximately 20-30 minutes per scan.

Randomization Procedures

After consenting, screening, and obtaining an MRI, participants will be block

Version 10 Revised 11/21/2014

randomized into groups (20 minute tDCS group + gait training or sham tDCS + gait training).

Baseline Procedures

The TMS motor threshold (MT) will be established²⁷ and the best location for eliciting MEPs from the contralesional TA muscle will be tracked on the subject's CT or MRI scan, or on a template MRI scan if clinical studies are not available, using Brainsight. Gait assessment (details provided in **Outcome Measures**) and the Stroke Impact Scale-16 will be performed for all participants at UCA. Motor evoked potentials and Recruitment curves (developed by the TMS procedure) will be performed at UAMS.

Intervention Procedures (Study Weeks 1 through 4)

Study interventions will be conducted 3 times a week for 4 continuous weeks. tDCS, and gait training will be performed at Movement Analysis Laboratory, Department of Physical Therapy, UCA as described above (**Study Interventions**).

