Post-Intervention Procedures (Study Weeks 5(± 5 days) and 8 (± 10 days) :

During Study Weeks 1-5, and 8 Gait assessment (details provided in **Outcome Measures**) and the Stroke impact Scale 16 will be performed at UCA. During Study Weeks 5 and 8 TMS will be performed at UAMS and participants will complete a repeat fMRI scan. Details of TMS procedure used to establish recruitment curves are located in the Outcome Measures.

Reduction of Study Bias:

[name] will supervise delivery of interventions, and so, he will not be blinded to tDCS condition; however, Drs. [name] and [name] who collect and analyze data will be blinded to condition.

Study Locations:

tDCS, gait training, SIS-16, and the assessments of gait will take place in the Motion Analysis Laboratory at UCA; motor evoked potentials and recruitment curves developed from TMS are measured in the TMS and Human Electrophysiology core facilities at UAMS. Subject burden is reduced by requiring only four trips to UAMS over two - three months. (Subjects are informed that scheduling conflicts could result in an extra visit.) UAMS will be the IRB of record and Sponsor of the IDE.

Study Schedule

	Screening	Baseline	Study Weeks 1 -4 ^b	Study Week 5	Study Week 8
Consent	X				
Screening	X				
NIH Stroke Scale	X				
Modified Rankin Scale	X				
TASS	X				
Medical Record Review	X				
MRI	X			X	
Pregnancy Assessment	X				
Randomization	X				
Assessments					
Gait assessments		X	X	X	X
RC & SIS		X		X	X
Interventions					
tDCS			X		
Sham tDCS			X		
Gait training			X		

Definitions: TASS= Transcranial Magnetic Stimulation Adult Safety Screen, MRI=magnetic resonance imaging, RC & SIS-16=recruitment curve established using transcranial magnetic stimulation (TMS) and Stroke Impact Scale . ^bThree times a week for four weeks participants will receive active or sham tDCS and gait training interventions at UCA for a total of 12 treatment periods.

Study Population

Up to 100 stroke patients will be enrolled to obtain 88 who meet entry criteria and complete study procedures (i.e., 44 participants in each of the active or sham tDCS groups). Attrition, estimated at about 15%, will be handled by replacement.

Participants will be ≥21 years old to better represent the general stroke population. All participants will complete the NIH Stroke Scale, have evidence of gait impairment, and will be able to fully and safely participate in treatment.

Inclusion Criteria

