Exploratory Aim. We will classify patients as “likely responsive” and “likely unresponsive” to tDCS based on the magnitude of difference scores and compare them to determined patient characteristics that predict a treatment response. Predictors for 88 subjects include 1) NIH Stroke Scale score, 2) initial levels of impairment, 3) initial MT of the contralateral TA muscle (and recruitment curve parameters from the ipsilateral TA muscle), 4) initial SIS-16 total and subscale scores, 5) stroke laterality, and 6) modified Rankin Scale scores. A series of regression analyses will be conducted to reduce the overall number of predictors and to build an initial model, which assess the predictive value or weight of remaining variables, and to cross-validate predictors. To determine which stroke related variables are associated with a response to treatment, brain lesions will be mapped onto templates and analyzed using lesion subtraction techniques with the public domain MRIcro and MRIcron software programs (see Core B). Lesion subtraction will identify the lesion sites that are common to treatment responders and not common to nonresponders.

Ethical Considerations

This study will be conducted in accordance with all applicable government regulations and University of Arkansas for Medical Sciences research policies and procedures. This protocol and any amendments will be submitted and approved by the UAMS Institutional Review Board (IRB) to conduct the study.

The PI or designated staff will discuss the informed consent form with the subject volunteer. The consent process will take place in a quiet and private room. Subjects may take as much time as needed to make a decision about their trial participation and may take the document home if desired. The person obtaining consent will thoroughly explain each element of the document and outline the risks and benefits, alternate treatment(s), and follow-up requirements of the study. Participation privacy will be maintained and questions regarding participation will be answered. No coercion or undue influence will be used in the consent process. No research related procedures will be performed prior to obtaining informed consent. All signatures and dates will be obtained. A copy of the signed consent will be given to the participant. The informed consent process will be documented in each subject’s research record.

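### The exploratory aim labels patients as responders to tDCS by their own change from baseline, with no arm comparison, so it does not separate predictors of tDCS benefit from predictors of improvement in either arm

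*Combined protocol and SAP*

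**What the plan says.** The Exploratory Aim paragraph of Data Analysis will classify patients as likely responsive or likely unresponsive "to tDCS based on the magnitude of difference scores and compare them to determined patient characteristics that predict a treatment response". The Aims 1-3 paragraph of the same section defines a difference score as change from baseline, so it is a within-patient quantity and not an active-minus-sham difference.

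The candidate predictors are given for the whole trial: "Predictors for 88 subjects include 1) NIH Stroke Scale score, 2) initial levels of impairment", followed by motor threshold and recruitment-curve parameters, "4) initial SIS-16 total and subscale scores", stroke laterality and modified Rankin score. Treatment arm is not on the list. The modelling is described as follows: "A series of regression analyses will be conducted to reduce the overall number of predictors and to build an initial model", with later weighting and cross-validation of the predictors that remain. For the imaging: "Lesion subtraction will identify the lesion sites that are common to treatment responders and not common to nonresponders".

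Study Population gives the split as "44 participants in each of the active or sham tDCS groups". Randomization Procedures gives the two arms as "20 minute tDCS group + gait training or sham tDCS + gait training", so gait training is common to both.

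The Protocol Summary and the Exploratory Aim under Specific Aims speak more loosely of response to treatment. Neither mentions a comparison between arms for this aim.

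**The concern.** An active patient's change mixes gait training, measurement error and whatever tDCS added. A sham patient's change contains no tDCS effect at all. A characteristic that predicts benefit from tDCS must predict the difference between active and sham outcomes, and the stated analysis never estimates that difference. Two errors follow:

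- A general prognostic factor can be reported as a predictor of tDCS response.
- A true modifier of the tDCS effect can be missed if it points the other way prognostically.

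The label matters because Background and Rationale cites a national call to fit restorative therapies to suitable patients and says this proposal answers it. A mislabelled factor could be read as grounds for choosing who receives tDCS.

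**Working it through.** The plan gives no outcome, visit, cut-off, power or alpha for this aim, so it has no figure to reproduce. The figures below are an illustration.

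**Inputs from the documents.** 44 per arm (Study Population); r = 0.60 and d = 0.39 (Power analysis, for gait speed); alpha 0.05, taken as two-sided.

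**Assumed.** Standard normal baseline and follow-up with correlation r; a standardised characteristic X with slope b in both arms; a median cut of change; b = 0.2, 0.3 or 0.4 SD per SD.

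**Step 1: a purely prognostic factor, no tDCS effect.** The noise in the change score has variance 2(1 − r) = 0.8. The correlation of X with change is ρ = b/√(b² + 0.8). A median split shrinks it by about √(2/π) = 0.798. Power is about Φ(z√(n − 3) − 1.96), where z = atanh(0.798ρ).

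For b = 0.3: ρ = 0.3/√0.89 = 0.318; 0.798 × 0.318 = 0.254; z = 0.259. With n = 88, 0.259 × √85 = 2.39, and Φ(0.43) = 0.67. With n = 44 (active patients only), 0.259 × √41 = 1.66, and Φ(−0.30) = 0.38. Simulation (10,000 trials per cell) agrees:

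| Analysis | b = 0 | 0.2 | 0.3 | 0.4 |
|---|---|---|---|---|
| One cut across both arms | 0.048 | 0.376 | 0.683 | 0.890 |
| Separate cut in each arm | 0.050 | 0.364 | 0.670 | 0.884 |
| Active patients only | 0.055 | 0.204 | 0.383 | 0.596 |
| Arm × X test, baseline-adjusted | 0.052 | 0.053 | 0.050 | 0.047 |

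Cutting within arms, or labelling active patients only, does not cure the problem. With a uniform tDCS effect of d = 0.39, the single cut flags X in 0.354, 0.655 and 0.867, and the interaction test in 0.046 to 0.051.

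**Step 2: closer to the planned modelling.** With six uncorrelated predictors, the pooled label and backward elimination at 5% (1,500 trials), the prognostic factor is retained in 0.364, 0.639 and 0.877. Retained factors pass 5-fold cross-validation in 98-100%. That figure is optimistic because selection used all the data, but a real prognostic factor should pass, so cross-validation does not protect against the wrong label.

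**Step 3: a true modifier missed.** Take an interaction of 0.39 with sham slope −0.2. The active slope is −0.2 + 0.39 = 0.19, and the pooled slope is (−0.2 + 0.19)/2 = −0.005. The pooled label flags it in 5% of trials and the interaction test in 59%. This is a near-cancelling case. At sham slopes −0.1, 0 and 0.1 the pooled label flags 11%, 30% and 59%, against about 59% for the interaction test.

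**Step 4: who the responders would be, if one cut spans both arms.** At d = 0.39 the sham share is Φ(−0.195/√0.8) = Φ(−0.218) = 0.41 (simulated 0.415). About four in ten patients labelled responsive to tDCS would never have received it.

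**Step 5: a conditional side point.** If the label uses an outcome whose own baseline is a listed predictor, such as SIS-16, regression to the mean makes that baseline look predictive. Its correlation with change has size √((1 − r)/2). It is flagged in 94%, 67%, 38% and 22% at r = 0.6, 0.8, 0.9 and 0.95. The plan gives no r for SIS-16 and names no outcome for the label. The baseline-adjusted interaction test stays at about 5%.

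**The case against.** The strongest defence is that the aim concerns response to treatment in general. The Protocol Summary, the Specific Aims and the rest of the Exploratory Aim paragraph can be read that way, and only one phrase names tDCS. On that reading the analysis can stand and only the wording is wrong. This is fair, and the first remedy below is built on it. It does not rescue the phrase itself.

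Next, the list of predictors is open-ended and the regressions are loosely described, so an arm term is not excluded. That is true, but nothing commits the trial to one. The only stated arm comparison belongs to Aims 1-3 and involves no patient characteristic.

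The sizes rest on assumed slopes, and using 0.39 as an interaction per SD borrows a number that the plan gives for a different purpose. That stands. The percentages show direction and order of size, and are not forecasts.

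Finally, an interaction test has low power, and the pooled label can flag more when a modifier is also prognostic. With prognostic slope 0.2 and interaction 0.39 it flags 0.825 against 0.597 at d = 0.39, and 84% against 59% at d = 0. This also stands, but such flags do not show whether the factor predicts recovery or benefit from tDCS. The aim's exploratory status excuses low power. It does not excuse an answer to a different question from the one on the label.

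**Conclusion.** The concern holds. As written, the rule would report prognostic factors as predictors of tDCS response. Under the assumptions above, a prognostic factor of modest to moderate strength is mislabelled in roughly 38% to 89% of trials with one cut across arms, or 20% to 60% with active patients only, against about 5% for an interaction test. The structural point needs none of these figures: change from baseline alone, without an active-sham contrast, cannot identify who benefits from tDCS.

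The reach is limited. The aim is exploratory, Aims 1-3 compare the arms and are untouched, and the randomised sham data needed for a correct analysis will already exist. The plan should be changed, but the trial's main conclusions do not depend on it.

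**What to change.** Choose one of two remedies.

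**(a) Reword.** In the Exploratory Aim paragraph, replace response to tDCS with response to the gait-training programme, and report the results as predictors of recovery. This costs a few words.

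**(b) Keep the tDCS question.**
- Name the outcome and visit.
- Model the continuous follow-up score adjusted for its baseline, and add arm and arm-by-predictor terms to the planned regressions.
- Call a characteristic a predictor of tDCS response only on its interaction, and report main effects as predictors of recovery.
- Give interactions with 95% confidence intervals as hypothesis-generating. Predictor reduction and cross-validation can stay, with a note that the intervals are not adjusted for selection.
- State how many randomised patients lack a follow-up score, because "Attrition, estimated at about 15%, will be handled by replacement".

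Under either remedy, show the lesion maps by arm or describe them as maps of improvement.

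Remedy (b) changes text only and needs no new data from followed patients. Its price is power. With 44 per arm and r = 0.6, the interaction has standard error about √(1 − 0.36) × √(2/44) = 0.171. An interaction of 0.39 gives 0.39/0.171 = 2.29 and power near Φ(0.33) = 63%; an interaction of 0.2 gives about 22%. Simulation puts these slightly lower, at 59% and 20%. At 0.05/6, for the six listed items, power is 32% and 6%. Several items contain more than one variable, and at an assumed 0.05/12 it falls to about 24% and 4%. If 15% were lost without replacement, which is not the plan (44 × 0.85 ≈ 37 per arm), power at 5% would be 51% and 17%. Wide intervals should be expected and reported as such.
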